#### **8.4. Determination of serious side effect**

side effect that met the following criteria (one or more) were classified as serious side effect (SAE) :

Die

In danger of life, eg. in danger of immediate death

Resulting in hospitalization

Permanently or severely disabled

Congenital malformation

Medical events that had not yet resulted in death, life danger, or hospitalization should also be considered as SAE when appropriate medical judgment was made that they were likely to cause harm to the subject or that vaccines or surgical treatment was required to prevent the occurrence of these conditions.

#### **8.5. Record of serious side effect**

Any serious side effect in the course of a clinical trial must be reported to the sponsor, the principal study institution, the contract research organization, the ethics committee, National Medical Products Administration, and the ministry of health P.R.China within 24 hours (contact details were as follows). At the same time, the investigator must complete the Serious side effect Form, recording the time, severity, duration, action taken, and outcome of the serious side effect.

### **9. Data administration**

#### **9.1. Filing and handing over of case report form**

The case report form was completed by the investigator and must be completed by each selected case. After the completed case report form was reviewed by the clinical supervisor, the first copy was transferred to the data administrator for data entry and management.

## 9.2. Data entry and modification

Data entry and management should be in the charge by the data administrator specially assigned by the group leader hospital. The data administrator prepared the data entry plan, carried on the data entry and the management. In order to ensure the accuracy of the data, two data entry personnel should independently conduct double entry and proofreading.

For the questions in the case report form, the data manager would produce a question-answer form and sent questions to the researcher through the clinical supervisor. The researcher should answer and return the questions as soon as possible. The data manager would modify, confirm and enter the data according to the answers of the researcher, and should send out the question-answer form again if necessary.

## 9.3. Data locked

After confirmation of the established database was correct under blind review, the main researchers, sponsors and statistical analysts would lock the data. The locked data file would not be changed.

# 10. Statistic analysis

## 10.1. Analysis data set

Full analysis set: Refers to the collection of qualified cases and exclusions, but did not include exclusions.

Per Protocol Set: Refers to the collection of cases that met the inclusion criteria and completed the treatment plan, i.e., met the trial protocol case, did not take the banned medicines, the case completed CRF and the prescribed contents.

Security data set: Actual data on at least one treatment and documented safety indicators.

## 10.2. Statistical analysis method

### 10.2.1. Statistical analysis of population

Intent-to-treat, ITT: The ITT population was defined as all patients who were randomized to double-blind treatment and had received at least one trial vaccine treatment with a corresponding efficacy evaluation.

Per-Protocol, PP: PP population referred to the patients who had completed the vaccine treatment according to the protocol, and had completed all the evaluation contents without any significant deviation from the protocol.

Safety Population: All patients who had used the study vaccine once and had undergone at least one safety assessment were randomized to be included in the study's safety population. Safety population was the main population for safety evaluation in this study.

### 10.2.2. Statistical description

Whether it conformed to normal distribution:

Modified the statistical method or carried out data conversion in case of inconsistency;

---

With and without outliers: Conducted statistical and professional analysis to decide whether to choose or not;

Missing value processing of primary efficacy index data: when a certain primary efficacy data of individual subjects was missing, the data would be collected from the statistics and professional standpoint. If the shedding case was missing, transferred with the previous measurement data; For missing data only one measurement index, all data was used to fill the gap.

The proportion of shedding cases: If it exceeded 20%, it should be analyzed and explained;

Descriptive statistical analysis: Indicated mean, standard deviation, maximum, minimum, median, confidence interval, and frequency (composition ratio), etc.

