### **5.3. Case withdrawal criteria**

Discontinuation of *Bacillus subtilis* spore due to side effect determined by the investigator;  
Discontinuation of *Bacillus subtilis* spore due to other reasons (including voluntary withdrawal);  
Unable to cooperate;  
For reasons other than research-related, the investigator did not consider it appropriate to continue the clinical trial.

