### **5.4. Management of cases of loss**

Definition of cases of loss: all subjects who had completed the informed consent form and were screened for entry into the study, at any time and for any reason withdrawal, as long as the subjects did not complete the observation period specified in the protocol, was called cases of loss, including the following conditions:

A serious side effect occurred in the subject and, in the judgment of the physician, the case should be discontinued.

During the study, the subjects' original condition worsened or other symptoms occurred during the study that affected the observation of the study, according to the doctors decided that the clinical trial should be stopped.

Significant deviations occurred during the implementation of the clinical trial protocol, making it difficult to evaluate the vaccine effect.

Subjects were unwilling to continue the clinical trial.

Treatment of cases of loss: contacted subjects with reasons, recorded the time of last observation, and completed the assessment items that could be completed. For patients who withdrew from the study due to allergy or other side effect and failure to respond to treatment, the investigator should take appropriate treatment measures according to the actual situation of the subjects. The researchers should properly preserved the relevant experimental data of the cases of loss, not only for filing, but also for carrying out the complete analysis set statistics.

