## 7. Clinical efficacy indexes and safety evaluation criteria

### 7.1. Main efficacy indicators

Immunogenicity of vaccines

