## 11. Quality control and assurance

### 11.1. Quality control

During the study, clinical inspectors will be commissioned by the sponsor to visit each study center regularly to ensure that all the contents of the study plan were strictly followed and the study data were filled in correctly.

The whole clinical trial process strictly followed the provisions of the national GCP (Good Clinical Practice) and conformed to the ethical principles. Participants might strictly abide by the standard operating procedures of clinical trial study.

Participants in clinical trials should be relatively fixed, and participants might undergo uniform training and had uniform recording methods and judgment criteria.

The researcher should fill in the CRF truthfully, carefully and use pen or carbon pen.

All observations and findings in clinical trials should be verified to ensure the reliability of the data and to ensure that the conclusions of clinical trials were derived from the original data. There were corresponding data management measures in clinical trial and data processing stage.

Medical records and medical record forms were regarded as the original records and generally could not be changed. When making any corrections, the original record should not be altered. Additional statement could be used to explain the reason, and then signed and dated by the physician participating in the clinical trial.

The researchers should take active measures (notice further consultation, follow up) to control the shedding rate within 20%.

Subjects would record their vaccination status on a diary card.

Each center should submit its normal range and abnormal judgment criteria to the responsible unit of clinical trial and the clinical statistical unit to ensure the accuracy, reliability and abnormal judgment criteria of laboratory examination.

All laboratory data should be recorded in the original medical record and the results of the tests should be glued to the original medical record. Laboratory data within the normal range should also be recorded in the CRF, and data that were significantly higher or outside the clinically acceptable range should be verified by the physician participating in the clinical trial to make the necessary statements.

Administration of vaccines:

Preservation conditions of experimental vaccine: under 23° C, sealed in a dark place.

---

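### The primary immunogenicity data are to be filled by carrying values forward or by an undefined rule, with no sensitivity analysis; this can bias later-visit results either way and undermine their intervals

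*Combined protocol and SAP*

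**What the plan says.** Section 10.2.2 has an item headed "Missing value processing of primary efficacy index data". For drop-outs it says: "If the shedding case was missing, transferred with the previous measurement data". For the other kind of gap it says: "For missing data only one measurement index, all data was used to fill the gap". It does not say which statistic computed from all data is inserted, or whether that is per visit, per group or overall.

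The primary index in section 7.1 is only "Immunogenicity of vaccines". No assay, scale, summary measure or primary time point is named. Sections 4.1 and 7.4 schedule examinations at D0, D7, D14, D21 and D28.

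On the amount of loss, section 11.1 says: "The researchers should take active measures (notice further consultation, follow up) to control the shedding rate within 20" per cent. Section 10.2.2 asks only for analysis and explanation above that level. Section 5.4 keeps the data of lost cases for the full-set statistics. Section 10.2.3 lists t, paired, rank and chi-square tests, and section 10.2.4 sets a two-sided 0.05 threshold. None of these sections allows for filled-in values.

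Two further rules bear on how gaps arise. Section 5.3 counts as withdrawal the stopping of the "spore due to side effect determined by the investigator". Section 5.4 counts as lost a case where "Significant deviations occurred during the implementation of the clinical trial protocol, making it difficult to evaluate the vaccine effect".

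**The concern.** A product intended to raise neutralising antibody should move the mean response between visits. A value carried from D7 to D28 therefore comes from a different point on the response curve. If the mean is still rising, the later-visit estimate is too low; if it has peaked and is falling, the estimate is too high. If there is a control group whose mean stays flat, the whole of that error passes into the group difference.

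The second rule raises a different problem. If the inserted value is an average, it adds no information but is counted as an observation, so the standard error is too small.

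At stake are the estimate, interval and P value for the main efficacy indicator. With no named sensitivity analysis, a reader of the results could not tell how much depends on the filling. The withdrawal and loss rules may also add gaps that continued follow-up would avoid.

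**Working it through.** The documents give no sample size, SD, expected response or expected drop-out rate, so there is no planned figure to reproduce. Every profile below is an assumption. The 20% comes from sections 10.2.2 and 11.1, where it is a ceiling on drop-out, not a forecast.

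**1. Carry-forward: bias in the D28 mean**

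D28 is used only because it is the last scheduled visit. With drop-out fraction d unrelated to response, and last visits spread evenly over D7, D14 and D21:

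estimate = (1 − d) × mean(D28) + d × average of the means at D7, D14 and D21.

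Mean log10 rise over D0, with d = 0.20:

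| Assumed profile (D0, D7, D14, D21, D28) | Estimate | Truth | Fold rise: estimate vs truth |
|---|---|---|---|
| Rising: 0, 0.1, 0.3, 0.5, 0.6 | 0.8 × 0.6 + 0.2 × 0.300 = 0.540 | 0.60 | 3.5 vs 4.0 |
| Peaked: 0, 0.4, 0.6, 0.4, 0.2 | 0.8 × 0.2 + 0.2 × 0.467 = 0.253 | 0.20 | 1.8 vs 1.6 |
| Flat: all 0 | 0 | 0 | 1.0 vs 1.0 |

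The loss pattern matters. If some subjects leave after D0 and the D0 value is carried forward (even spread over D0 to D21), the rising case becomes 0.8 × 0.6 + 0.2 × 0.225 = 0.525 (3.3-fold) and the peaked case 0.8 × 0.2 + 0.2 × 0.35 = 0.23 (1.7-fold). D7 to D21 is the main case because the ITT definition in section 10.2.1 requires an efficacy evaluation, so subjects with D0 data only may not be included.

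**2. Carry-forward: interval width and coverage**

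Simulation with 5,000 runs, n = 100, log2 scale, SD 1.5, correlation 0.7 between adjacent visits decaying with distance, and 20% random drop-out (all assumed):

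- Mean rising 1 log2 unit per visit, all losses after D21: bias −0.20, coverage of a nominal 95% interval 76%, width 0.92 of the observed-case width.
- Same profile, losses spread over D0 to D21: bias about −0.50, coverage about 23–25%, width about 1.1 times the observed-case width.
- Mean falling 1 log2 unit from D21 to D28, all losses after D21: bias +0.20, coverage about 75%, width 0.92.
- Flat mean: no bias, coverage about 95%, width 0.89.

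Under carry-forward, coverage is lost mainly through bias. The interval may be wider or narrower than the observed-case one. In the flat case it is narrower and still covers properly.

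**3. The second rule, read as filling with the observed mean (assumption)**

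Let m of n values be observed. Filled values add nothing to the sum of squares, so:

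filled SE / observed-case SE = √[(m − 1)/(n − 1)] × √(m/n) ≈ m/n.

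For n = 100, m = 80: √(79/99) × √0.8 = 0.80.

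Coverage of a nominal 95% interval ≈ 2Φ(1.96 × m/n) − 1, if the gaps are completely at random:

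- 10% filled: 2Φ(1.764) − 1 = 92.2%, a test error rate of about 7.8%.
- 20% filled: 2Φ(1.568) − 1 = 88.3%, a test error rate of about 11.7%.

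The mean itself is unbiased under that condition. The 20% in the documents concerns drop-outs, who fall under the first rule, so the 10% and 20% used here are purely illustrative.

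**The case against.** A reader might infer that the plan's rules certainly bias the D28 titre and certainly make its 95% interval too narrow. The documents do not support that. They name no titre, no primary time point and no interval level. Bias and narrowing are also separate effects: carry-forward can bias while giving a wider interval, mean filling narrows without bias under random loss, and a flat profile with carry-forward shows neither bias nor loss of coverage.

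A reader might also attach the 88% coverage to the tolerated 20% drop-out. That would apply the drop-out rate to a rule for a different kind of gap, on one reading of unclear text.

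Nor do the documents say that an investigator who can see immunogenicity results decides who is lost. The one-arm text suggests an open study, but sections 9.3 and 10.2.1 refer to blind review and double-blind treatment. Section 5.4 speaks of significant protocol deviations and asks that assessments which can still be done are completed.

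The per-protocol set requires completed evaluations, so it comes close to an observed-data analysis, and section 10.2.6 promises an analysis plan before database lock. Both points are fair but limited. The per-protocol set is not offered as a check on the filling and also selects on adherence. A later plan does not cancel a rule already written.

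The section 5.3 point depends on dosing. Sections 4.1 and 4.2 describe a single administration, while section 3 of the Summary and section 6.3 describe once-daily use. With a single dose, stopping the product would create few gaps.

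**Conclusion.** The concern stands in a limited form. The plan prescribes single imputation for its primary data: one rule that is biased whenever the mean is still changing after a drop-out's last visit, and one that cannot be carried out as written because the inserted statistic is not named. Filled values are then analysed as if observed, with no labelled sensitivity analysis.

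At 20% drop-out the illustrated bias is −0.06 or +0.05 on the log10 scale, in a direction that cannot be known in advance. It is zero if the response is flat. Under-coverage from the second rule is conditional on reading it as a mean fill, and its size cannot be fixed without a rate for such gaps.

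Confidence is high that the rules are there and unsuitable, and lower for any particular size. The plan should be changed before the database is locked.

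**What to change.** - Delete both fill-in rules in section 10.2.2. Analyse observed values only, with a mixed model for repeated measures on log-transformed immunogenicity, visit as a factor and an unstructured covariance. Pre-specify a simpler structure in case that does not converge, since no sample size is stated. State the missing-at-random assumption.
- Name the assay, scale and primary time point in section 7.1, because the model needs them.
- Report observed-case results as a sensitivity analysis. Add an analysis counting drop-outs as non-responders only if a responder definition is pre-specified; the documents have none.
- In sections 5.3 and 5.4, distinguish stopping the product from leaving the study, and keep collecting the already scheduled D7 to D28 assessments unless consent is withdrawn. This does not alter when product is stopped. The conflict between single and once-daily dosing must be reconciled separately.

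The cost is analysis text, one model, a small protocol wording change with continued scheduled follow-up, and possibly somewhat wider intervals; the mixed model's own precision was not computed here.

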#### 10.2.3. Analytical method

The experimental group was compared with the control group by superiority comparison.

Measurement data:  $X^2$  test, t-test, paired t-test, rank sum test, paired rank sum test and non-parameter test were used respectively statistical analysis to make statistical comparison and other methods.

Descriptive statistical analysis of side effect was performed.

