### 4. Overall design of test

This study was conducted in a single arm design.

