## 3. Test objective

The efficacy and safety of " Bacillus subtilis spore " were evaluated with simulated tablet as control

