## 4. Overall design and arrangement of the test

### 4.1. Test design

This study adopted a one-arm experimental design. The whole study mainly collected qualified normal healthy people without disease from the hospital, and excluded people with basic diseases such as hypertension, diabetes, hyperlipidemia and so on. Once confirmed, they were assigned to administer 1 dose of Bacillus subtilis spore. Follow-up observation and efficacy examination were performed on days 7, 14, 21 and 28.

If subjects had significant laboratory abnormalities or side effect at the end of the study, they should be followed up to normal.

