### 4.2. Dose, method and course of treatment

Group	Dosage	Usage	Survey
Test group	1 Bacillus subtilis spore capsule at a time	Oral administration, once	28 days

Vaccine time window: Oral administration of the vaccine would be given immediately after the subjects were selected.

Essential medicines: over-the-counter medicines such as vitamins and minerals were allowed.

---

Medicines prohibited: antibiotics, thrombolytic drugs, anticoagulants, insulin,  $\beta$ -blockers, adenosine preparations, leucocyte adhesion inhibitors, other antioxidants, free radical scavengers, etc.

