### **6.3. Administration**

Test group: Oral approach, 1 capsule B. subtilis spore once a day. No other medication.

Start in the morning on an empty stomach.

Control group: Oral approach, 1 simulated tablet once a day. No other medication.

Start in the morning on an empty stomach.

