#### 7.2.1 Immunogenicity of vaccines:

To test the immunogenicity induced by oral vaccine

Compared vaccine-induced immunogenicity with natural infection immunogenicity

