#### 10.2.6. Contents of statistical analysis

The statistical analysis plan was written by the statistician, finalized before the database lock, and consisted of a variety of tables. The main contents of the analysis included:

Case distribution: different data sets in each group, case distribution in each center, comparison of total abscission rate, and detailed list of termination causes.

Comparability analysis: compared demographic data with other base-value indicators to measure the comparability of the two groups.

Effectiveness analysis:  $X^2$  test and t test were used for main indicators and global indicators. Since this study was a multi-center clinical trial, central effect on the efficacy indicators should be considered in the analysis.

Analysis of the factors affecting the efficacy: such as age, sex, disease type, disease condition and so on, there were significant differences between the two groups before the use of vaccine, or if there were significant related factors that affected the vaccine effect, these factors should be used as co-factors when comparing the vaccine effect between the two groups for variables,

---

covariance analysis or Logistic regression analysis was required. The combination of medication and so on needed a detailed list.

Safety analysis: firstly, according to the requirements of side effect correlation, the side effect and adverse reactions of the two groups were listed and described (including the number of cases of various side effects, the number of cases and the conversion rate of "normal to abnormal" or "abnormal intensification" of laboratory test indicators before and after the test), and the reasons and explanations were listed.

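### The protocol contradicts itself on whether a control arm exists; under its stated single-arm design the superiority comparison, the two-group analyses and the ITT set cannot be carried out

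*Combined protocol and SAP*

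**What the plan says.** **Single arm.** The Summary (item 4) states: "This study was conducted in a single arm design". Section 4.1 repeats it: "This study adopted a one-arm experimental design". The table in 4.2 has one row, the test group, with the dosage given as "1 Bacillus subtilis spore capsule at a time".

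**Controlled.** The objective in section 3 says that efficacy and safety "were evaluated with simulated tablet as control", and item 2 of the Summary says the same in substance. Section 6.3 describes a second group: "Control group: Oral approach, 1 simulated tablet once a day". Sections 6.4 and 11.1 require quality checks on control tablets. Section 7.2.3 records deaths by group, and 7.4.1 has random numbers assigned at the start. The ITT population in 10.2.1 consists of patients randomised to double-blind treatment, and the safety population there also refers to randomisation.

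**Analysis.** Section 10.2.3: "The experimental group was compared with the control group by superiority comparison". It then lists the chi-square test, t test, paired t test, rank sum test and paired rank sum test. Section 10.2.6, which throughout speaks of two groups, adds that the chi-square "test and t test were used for main indicators and global indicators".

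**Natural infection.** Section 7.2.1 includes the item "Compared vaccine-induced immunogenicity with natural infection immunogenicity".

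**The concern.** The main efficacy analysis and the analysis set that carries it both depend on a group that the design sections say is not there. If the trial runs as 4.1 describes, the analyst reaches database lock with a superiority comparison that has no second group and an ITT definition that no subject meets, since nobody was randomised to double-blind treatment. A different analysis would then have to be chosen after the data exist.

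The claim is also at stake. A single-arm study can report change from baseline. It cannot report superiority over a simulated tablet, although the objective and 10.2.3 lead a reader to expect that.

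Two gaps sit beside this. Section 10.2.3 does not tie any listed test to an endpoint, visit or contrast. The natural-infection comparison names no source for its comparator.

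**Working it through.** The documents state no sample size, power, effect size, standard deviation, allocation ratio or margin. There is no figure to reproduce, and the check is a reading of the sections against each other.

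**Step 1. Is there a control arm?**

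| Section | Points to |
|---|---|
| Summary item 4; 4.1 | one arm |
| 4.2 table | test group only |
| Summary item 2; 3 | simulated-tablet control |
| 6.3 | control group with its own regimen |
| 6.4; 11.1 | control tablets held at the centre |
| 7.2.3 | more than one group |
| 7.4.1 | random numbers |
| 10.2.1 | randomised, double-blind |
| 10.2.3 | superiority over control |
| 10.2.6 | two groups |

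The table of contents also lists a control-tablet section (6.2) and a chapter on blinding and randomisation (8). The body has neither: its 6.2 is packaging and its chapter 8 is side effects. That would fit controlled-trial wording left in a single-arm protocol, but it does not prove it, because 6.3 still describes a control group. The body gives no randomisation method, allocation ratio or group size.

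**Step 2. What can be run under each reading?**

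| Planned element | Single arm | Control group enrolled |
|---|---|---|
| Superiority comparison (10.2.3) | no comparator; cannot be run | possible in principle; endpoint, visit and allocation missing |
| Two-group comparability, efficacy and safety analyses (10.2.6) | cannot be run | possible |
| ITT set (10.2.1) | no subject qualifies | usable if randomisation and blinding are real |
| Change from D0 | possible; not stated as the main contrast | possible; secondary to the group comparison |
| Comparison with natural infection (7.2.1) | comparator undefined | comparator undefined |

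**Step 3. Which test goes with which contrast?** Section 7.4 schedules all trial indicators on the same people at D0, D7, D14, D21 and D28. Section 7.1 names immunogenicity as the main indicator, without assay, visit or summary measure. Section 10.2.3 offers paired and unpaired tests together. Section 10.2.6 names only chi-square and t test for the main indicators, in a two-group context and without mention of pairing. From this text two analysts could choose different visits, measures and tests and both claim to follow the plan.

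**Step 4. Natural infection.** Section 4.1 recruits healthy people only. No convalescent sample, historical dataset or reference standard is described, so the item in 7.2.1 has no defined second term.

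**The case against.** The strongest reply is that the single-arm statement should not be treated as settled. Section 6.3 gives a control group its own regimen, and 6.4 and 11.1 provide for control tablets. If that group is enrolled, a superiority comparison is possible. This stands. A reader might infer that the trial certainly has no control subjects, and the documents do not support that. They support a contradiction, and a conclusion conditional on the design statements.

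A second reply concerns the tests. A reader might infer that the plan would apply independent-group tests to before/after data. It does not say so: 10.2.3 lists the paired t test and paired rank sum test, and the tests named in 10.2.6 sit in two-group text where they would be a normal choice. What remains is the missing link from test to endpoint, visit and contrast.

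Third, 7.2.1 does not promise an enrolled convalescent group or a formal test. An external reference could serve. This also stands; the gap is that no source is named.

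Fourth, 10.2.6 has a statistician finalise the analysis plan before database lock, and 10.1 defines a full analysis set without reference to randomisation. A later plan could assign the tests and choose the set. It could not supply a missing control group, and it would have to depart from 10.2.3 to be executable.

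**Conclusion.** The point holds as an internal contradiction with a conditional consequence, and it must be resolved before analysis. Under the design stated in the Summary, 4.1 and 4.2, the superiority comparison in 10.2.3, the two-group analyses in 10.2.6 and the ITT set in 10.2.1 cannot be carried out, and superiority over control cannot be concluded. Under the controlled reading they become possible, but the primary endpoint, visit, allocation and sample size are still not stated. The undefined natural-infection comparator and the unassigned tests apply under both readings.

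The consequence is that the main contrast and its population fail as written. A reader might want to attach a loss of power or a false-positive rate to this. The documents give no sample size, variability, within-subject correlation or assay schedule, so any such figure would rest wholly on invented inputs, and none is offered. The conclusion assumes nothing beyond the wording of the sections cited.

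**What to change.** First reconcile the design sections (Summary items 2 and 4; 3; 4.1; 4.2; 6.3; 7.4.1; 10.2.1; 10.2.3; 10.2.6) so that they all describe the trial actually being run.

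**If single-arm:**
- Replace the superiority and two-group text with one prespecified primary contrast: within-subject change from D0 to a single named visit (for example D28) in log10 neutralising antibody. Report the geometric mean fold rise with a 95% CI from a paired t test.
- Use the signed-rank test as sensitivity analysis, and an exact binomial CI for the seroconversion proportion.
- Redefine the ITT and safety sets without randomisation or blinding.
- Limit the objective and the conclusions to change from baseline.

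**If a control group is enrolled:**
- Correct the Summary, 4.1 and 4.2, and state the allocation.
- Compare groups by ANCOVA on log10 titre at the named visit, with the D0 titre as covariate.

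**In either case:** label the natural-infection comparison descriptive and name its source, or delete it.

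The cost is rewording of the protocol and analysis plan. Under the single-arm version the claim becomes weaker: a rise from baseline in place of superiority over control.
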